5.4.3 Reporting Requirements for Pregnancies

5.4.3.1 Pregnancies in Female Patients

Female patients of childbearing potential will be instructed to immediately inform the investigator if they become pregnant during the study or within 8 weeks after the *final* dose of study drug. A paper Clinical Trial Pregnancy Reporting Form should be completed and submitted to the Sponsor or its designee immediately (i.e., no more than 24 hours after learning of the pregnancy), either by faxing or by scanning and emailing the form using the fax number or email address provided to investigators. Pregnancy should not be recorded on the Adverse Event eCRF. The investigator should discontinue study drug and counsel the patient, discussing the risks of the pregnancy and the possible effects on the fetus. Monitoring of the patient should continue until conclusion of the pregnancy. Any serious adverse events associated with the pregnancy (e.g., an event in the fetus, an event in the mother during or after the pregnancy, or a congenital anomaly/birth defect in the child) should be reported on the Adverse Event eCRF. In addition, the investigator will submit a Clinical Trial Pregnancy Reporting Form when updated information on the course and outcome of the pregnancy becomes available.

5.4.3.2 Pregnancies in Female Partners of Male Patients

Male patients will be instructed through the Informed Consent Form to immediately inform the investigator if their partner becomes pregnant during the study or within 8 weeks after the *final* dose of study drug. A paper Clinical Trial Pregnancy Reporting Form should be completed and submitted to the Sponsor or its designee immediately (i.e., no more than 24 hours after learning of the pregnancy), either by faxing or by scanning and emailing the form using the fax number or email address provided to investigators. Attempts should be made to collect and report details of the course and outcome of any pregnancy in the partner of a male patient exposed to study drug. When permitted by the site, the pregnant partner would need to sign an Authorization for Use and Disclosure of Pregnancy Health Information to allow for follow-up on her pregnancy. If the authorization has been signed, the investigator should submit a Clinical Trial Pregnancy Reporting Form when updated information on the course and outcome of the pregnancy becomes available. An investigator who is contacted by the male patient or his pregnant partner may provide information on the risks of the pregnancy and the possible effects on the fetus, to support an informed decision in cooperation with the treating physician and/or obstetrician.

5.4.3.3 Abortions

Any abortion should be classified as a serious adverse event (as the Sponsor considers abortions to be medically significant), recorded on the Adverse Event eCRF, and reported to the Sponsor immediately (i.e., no more than 24 hours after learning of the event; see Section [5.4.2](#)).

5.4.3.4 Congenital Anomalies/Birth Defects

Any congenital anomaly/birth defect in a child born to a female patient exposed to study drug or the female partner of a male patient exposed to study drug should be classified as a serious adverse event, recorded on the Adverse Event eCRF, and reported to the Sponsor immediately (i.e., no more than 24 hours after learning of the event; see Section 5.4.2).

5.5 FOLLOW-UP OF PATIENTS AFTER ADVERSE EVENTS

5.5.1 Investigator Follow-Up

The investigator should follow each adverse event until the event has resolved to baseline grade or better, the event is assessed as stable by the investigator, the patient is lost to follow-up, or the patient withdraws consent. Every effort should be made to follow all serious adverse events considered to be related to study drug or trial-related procedures until a final outcome can be reported.

During the study period, resolution of adverse events (with dates) should be documented on the Adverse Event eCRF and in the patient's medical record to facilitate source data verification.

All pregnancies reported during the study should be followed until pregnancy outcome.

5.5.2 Sponsor Follow-Up

For serious adverse events, adverse events of special interest, and pregnancies, the Sponsor or a designee may follow up by telephone, fax, email, and/or a monitoring visit to obtain additional case details and outcome information (e.g., from hospital discharge summaries, consultant reports, autopsy reports) in order to perform an independent medical assessment of the reported case.

5.6 ADVERSE EVENTS THAT OCCUR AFTER THE ADVERSE EVENT REPORTING PERIOD

The Sponsor should be notified if the investigator becomes aware of any **serious** adverse event that occurs after the end of the adverse event reporting period (defined as 16 weeks after the last dose of study drug), if the event is believed to be **related** to prior study drug treatment. These events should be reported through use of the Adverse Event eCRF. However, if the EDC system is not available, the investigator should report these events directly to the Sponsor or its designee, either by faxing or by scanning and emailing the paper Clinical Trial Serious Adverse Event/Adverse Event of Special Interest Reporting Form using the fax number or email address provided to investigators.

5.7 EXPEDITED REPORTING TO HEALTH AUTHORITIES, INVESTIGATORS, INSTITUTIONAL REVIEW BOARDS, AND ETHICS COMMITTEES

The Sponsor will promptly evaluate all serious adverse events and adverse events of special interest against cumulative product experience to identify and expeditiously

communicate possible new safety findings to investigators, IRBs, ECs, and applicable health authorities based on applicable legislation.

To determine reporting requirements for single adverse event cases, the Sponsor will assess the expectedness of these events using the following reference document:

- Crenezumab Investigator's Brochure
- *PET Ligand Investigator's Brochures*

The Sponsor will compare the severity of each event and the cumulative event frequency reported for the study with the severity and frequency reported in the applicable reference document.

Reporting requirements will also be based on the investigator's assessment of causality and seriousness, with allowance for upgrading by the Sponsor as needed.

6. STATISTICAL CONSIDERATIONS AND ANALYSIS PLAN

The safety analysis population will include all patients who consented to the OLE study, including those who enrolled in the OLE but did not receive open-label treatment. The intent-to-treat (ITT) population includes all patients who consented to the OLE study and received at least one dose of open-label treatment.

Safety will be assessed by monitoring adverse events, clinical laboratory evaluations, clinical assessments such as ECG and vital signs measurements, MRI evaluations and immunogenicity as measured by ADAs. Patients will be analyzed according to actual treatment received. All safety data will be summarized using descriptive statistics.

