- Inability to tolerate MRI procedures or contraindication to MRI, including, but not limited to, presence of pacemakers not compatible with MRI, aneurysm clips, artificial heart valves, ear implants, or foreign metal objects in the eyes, skin, or body that would contraindicate an MRI scan; or any other clinical history or examination finding that, in the judgment of the investigator, would pose a potential hazard in combination with MRI
- Pregnant or lactating, or intending to become pregnant during the study

- Any other severe or unstable medical condition that, in the opinion of the investigator or Sponsor, could be expected to progress, recur, or change to such an extent that it could put the patient at special risk, bias the assessment of the clinical or mental status of the patient to a significant degree, or interfere with the patient's ability to complete the study assessments
- Chronic use of anticoagulants or participation in any other investigational drug treatment trial

See the protocol for further details and other concomitant medication restrictions.

End of Study

The end of this study is defined as the date when the last patient, last visit occurs or the date at which the last data point required for statistical analysis or safety follow-up is received from the last patient, whichever occurs later. The end of the study is expected to occur approximately 28 months after the last patient is enrolled.

Length of Study

The total length of the study, from screening of the first patient to the end of the study, is expected to be approximately 4 years.

Investigational Medicinal Products

Test Product (Investigational Drug)

Crenezumab will be administered via IV infusion to all patients at a dose of 60 mg/kg Q4W until the end of the study.

Statistical Methods

Primary Analysis

The safety analysis population will include all patients who completed the double-blind treatment period and received at least one dose of study drug in either Study BN29552 or BN29553 and entered the OLE study. Patients will be grouped according to the treatment actually received until the first visit of the OLE study.

- Incidence, nature, and severity of adverse events
- Incidence, nature, and severity of serious adverse events
- Incidence of adverse events of special interest
- Incidence and nature of MRI safety findings: ARIA-E and ARIA-H
- Incidence of treatment discontinuations due to adverse events

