3.2 STUDY DESIGN

All patients who are enrolled in the OLE study will receive crenezumab 60 mg/kg administered by IV infusion Q4W.

Data collected at Week 105 of the DBTP of Studies BN29552 and BN29553 and results from a coagulation blood test taken before the first OLE infusion will be used to assess patient eligibility for the OLE study. This Week 105 data will also be used as OLE baseline data.

Prior to administering the first infusion in the OLE, eligibility will be ensured by reviewing Week 105 assessment results (*including MRI results*), *OLE screening* coagulation blood test results, and any other significant patient changes.

Once a patient is identified as eligible for the OLE study, the following will occur:

- Patients can receive the first infusion of crenezumab at any time on or up to 8 weeks after the Week 105 visit of the double-blind studies. Any extensions to this period must be approved by the Sponsor. Sites can arrange an infusion visit as soon as *eligibility assessment results* are available (including MRI results and results from the coagulation test) to assess OLE eligibility. Details of the visit schedule and associated assessments are given in [Appendix 1](#).
- The day that the first dose of crenezumab is administered will be Visit 1, Week 1 of the OLE.
- On Visit 1, Week 1 of OLE (i.e., the first open-label infusion of crenezumab), safety assessments must be done as indicated in the schedule of activities (see [Appendix 1](#)).

For details on the schedule of activities, see [Appendix 1](#). For details on the length of the study, see Section [3.3](#).

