5.3.1 Adverse Event Reporting Period

Investigators will seek information on adverse events at each patient contact. All adverse events, whether reported by the patient or noted by study personnel, will be recorded in the patient's medical record and on the Adverse Event eCRF.

After informed consent has been obtained but prior to initiation of study drug, only serious adverse events caused by a protocol-mandated intervention (e.g., invasive procedures such as biopsies, discontinuation of medications) should be reported (see Section 5.4.2 for instructions for reporting serious adverse events).

After initiation of study drug, all adverse events will be reported until 4 elimination half-lives after the last dose of study drug and collected on the occasion of the safety follow-up visit (16 weeks after the last dose of study drug).

Instructions for reporting adverse events that occur after the adverse event reporting period are provided in Section 5.6.

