5.4.2 Reporting Requirements for Serious Adverse Events and Adverse Events of Special Interest

5.4.2.1 Events That Occur prior to Study Drug Initiation

After informed consent has been obtained but prior to initiation of study drug, only serious adverse events caused by a protocol-mandated intervention should be reported. Investigators should *report* to the Sponsor or its designee immediately (i.e., no more than 24 hours after learning of the event).

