6.2 SUMMARIES OF CONDUCT OF STUDY

Enrollment, patient disposition, and incidence of protocol deviations will be summarized descriptively for the ITT population.

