6.4 SAFETY ANALYSES

The safety analysis population will include all patients who completed the DBTP and received at least one dose of study drug in either Study BN29552 or BN29553 and entered the OLE study. Patients will be grouped according to the treatment actually received until the first visit of the OLE study.

- Incidence, nature, and severity of adverse events
- Incidence, nature, and severity of serious adverse events
- Incidence of adverse events of special interest
- Incidence and nature of MRI safety findings: ARIA-E and ARIA-H
- Incidence of treatment discontinuations due to adverse events
- Mean changes in clinical laboratory tests from baseline over time, incidence of treatment-emergent abnormal laboratory values, and abnormal laboratory values reported as adverse events
- Mean change in ECG assessments from baseline over time and incidence of abnormal ECG assessments
- Incidence of immunogenicity as evidenced by antibodies to crenezumab or other components of drug product
- Mean change in vital signs (blood pressure, heart rate) from baseline over time and incidence of abnormal vital sign measurements
- Changes in CSSR-S scores from baseline over time.

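### The safety analysis population for the primary objective has two conflicting definitions, and only one of them expressly counts patients who never received open-label crenezumab

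*Combined protocol and SAP*

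**What the plan says.** Section 6 opens by defining the safety analysis population as "all patients who consented to the OLE study, including those who enrolled in the OLE but did not receive open-label treatment". The same paragraph requires an open-label dose only for the set it calls ITT. It then says that patients are analysed by the treatment they actually received, without naming the period.

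Section 6.4 gives a different rule: "The safety analysis population will include all patients who completed the DBTP and received at least one dose of study drug in either Study". The sentence goes on to name the two parent studies and makes entry into the OLE the last condition. On grouping it adds: "Patients will be grouped according to the treatment actually received until the first visit of the OLE study". The Synopsis, under Primary Analysis, repeats this rule: "The safety analysis population will include all patients who completed the double-blind treatment period and received at least one dose of study drug in". That sentence, too, names the parent studies and closes with OLE entry.

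Three other provisions bear on the point:

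- Section 3.2 fixes the first OLE visit: "The day that the first dose of crenezumab is administered will be Visit 1, Week 1 of the OLE".
- Section 5.3.1 limits event collection before that day: "After informed consent has been obtained but prior to initiation of study drug, only serious adverse events caused by a protocol-mandated intervention" are to be reported. Section 5.4.2.1 says the same.
- Section 6.2 restricts the conduct summaries: "Enrollment, patient disposition, and incidence of protocol deviations will be summarized descriptively for the ITT population". Section 6.3 likewise gives baseline characteristics for the ITT set.

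**The concern.** The denominator of the primary analysis should be fixed in advance and should have one definition. Here, an analyst working from Section 6 and another working from Section 6.4 could each follow the plan and report different denominators.

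Consented but undosed patients are foreseeable. Consent precedes any OLE-specific procedure (Section 4.5.11). The coagulation test follows consent (Appendix 1, footnotes b and f), and a persistently abnormal result excludes the patient (Section 4.1.2). The first infusion may fall up to 8 weeks after the parent-study Week 105 visit (Section 3.2). Section 4.5.11 itself provides for consent forms of patients who are not later enrolled.

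Such patients can contribute almost no events, because of the restricted collection before the first dose. If they enter the denominator, they dilute crude incidences. They would also be missing from the disposition and baseline summaries, which are confined to the dosed ITT set, so a reader could not see how many of them had been counted.

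**Working it through.** **The definitions side by side**

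| Condition | Section 6, safety | Section 6.4 and Synopsis, safety | Section 6, ITT |
|---|---|---|---|
| Consent to OLE | required | implied by entry | required |
| Completed double-blind period | not stated | required | not stated |
| At least one parent-study dose | not stated | required | not stated |
| Entered OLE | not stated | required, not defined | not stated |
| At least one open-label dose | expressly not required | not stated | required |

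The Section 6.4 set appears to lie within the Section 6 set. The two differ at least by consented patients who never entered the OLE, and by all undosed patients if entry means dosing.

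**The plan's own figure.** Section 6.1 expects about 925 patients: 1500 × (1 − 0.35) × (1 − 0.05) = 926.25. The figure reproduces and is not in dispute.

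**Size of the dilution.** Let u be the fraction of the safety denominator never dosed, p the event proportion among dosed patients, and q the proportion of undosed patients with a reportable pre-dose event. Then

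reported incidence = p(1 − u) + q·u.

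With q = 0 this is p(1 − u). For serious adverse events q may exceed 0, because those caused by a protocol-mandated intervention are collected before dosing. Incidence is then still diluted as long as q < p.

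The documents give no u, so 1%, 5% and 10% are assumptions. The rate p = 3.2% is the Phase II pneumonia rate in Section 1.2.3.3, used only for scale. The standard error at n = 925 is √(0.032 × 0.968 / 925) = 0.579 percentage points.

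| Assumed u | Undosed of 925 | Reported rate (q = 0) | Shift, points | Shift / SE |
|---|---|---|---|---|
| 1% | 9 | 3.17% | 0.03 | 0.06 |
| 5% | 46 | 3.04% | 0.16 | 0.28 |
| 10% | 93 | 2.88% | 0.32 | 0.55 |

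A shift of one standard error would need u = 0.579 / 3.2 = 18.1%.

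The relative loss is u at every event rate, but the shift in points grows with the rate. At the 91.1% overall adverse event rate of the Phase II crenezumab arms (Section 1.2.3.1), the same three values of u give 90.2%, 86.5% and 82.0%. The standard error there is √(0.911 × 0.089 / 925) = 0.94 points, so even u = 1% (0.91 points) is about one standard error. The 0.55 limit therefore applies to events about as rare as pneumonia, not to the overall adverse event rate.

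**The case against.** The best defence is that Section 6.4 and the Synopsis agree with each other and are specific to the primary safety analysis, whereas Section 6 is a general preamble. On that view the specific text governs. Because Section 3.2 makes the first-dose day Visit 1, entry into the OLE may also presuppose a dose, in which case nothing is diluted. This is a reasonable way to reconcile the text, but the plan states neither that precedence nor that meaning of entry. If entry does mean dosing, the conflict with the express inclusion of undosed patients in Section 6 becomes sharper.

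Second, Section 6 also says that patients are analysed by actual treatment received. A patient with no open-label dose has no OLE treatment and need not appear in a treated column. This stands: the dilution is conditional. It arises if undosed patients are grouped by parent-study treatment, as in Section 6.4, or are pooled with the rest.

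Third, a reader might infer that the error always makes the drug look safer. The documents do not support that. Pre-dose serious events caused by protocol procedures are reportable, so the direction for serious adverse events depends on how many occur. Nor do they support extending the dilution to ARIA or anti-drug antibody incidence. The OLE denominators for these are not stated, and Section 1.2.4 describes a denominator of treated patients with postbaseline samples for antibodies in earlier studies.

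Finally, the text defers several details to an SAP (Sections 1.3.3, 6.5, 6.5.2 and 6.6). None of those deferrals mentions the safety population.

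**Conclusion.** The conflict is real and plain from current text: the primary-objective population has two definitions and no rule of precedence. Confidence in that is high.

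Confidence in the size of the consequence is low. It rests on an undosed fraction that the documents do not give, and on undosed patients being counted in parent-arm or pooled columns. Under those conditions crude adverse event and special-interest event incidences fall by the factor (1 − u). Serious adverse event incidence would generally fall as well, unless offset by pre-dose events. For an event near 3.2% the shift is at most 0.32 points when u is 10% or less. The effect is probably small provided that few consenting patients go undosed. Safety is summarised descriptively, so no test result changes. Severity: minor.

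**What to change.** Use one definition in the Synopsis, Section 6 and Section 6.4: all patients who received at least one dose of open-label crenezumab, grouped by the treatment actually received in the parent study. Delete the Section 6 clause that brings in patients without open-label treatment. State that this set then coincides with the Section 6 ITT set apart from grouping, and say how a patient with no parent-study dose would be grouped.

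Amend Section 6.2 so that enrollment and disposition are summarised for all consented patients, with the number never dosed shown. List separately any pre-dose serious adverse events in those patients. Without the Section 6.2 change, undosed patients could not appear in a summary confined to dosed ones.

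Two clarifications belong with this:

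- In Section 6.4 and the Synopsis, replace completion of the double-blind period with completion of the Week 105 visit. Section 3.1 admits patients who stopped parent-study treatment early but reached that visit.
- State that the Section 6.3 sentence placing all randomized patients, as assigned, in the primary and exploratory analyses does not apply to safety.

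The delayed-start analysis in Section 6.5.2 already names its populations and needs no change. The cost is wording, one listing and one added count in the disposition table, with no new data collection. Compared with following Section 6 literally, reported incidences would generally be slightly higher, and pre-dose serious events in undosed patients would move from the main tables to the listing.

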6.1 DETERMINATION OF SAMPLE SIZE

This study is open to all patients who completed Study BN29552 or BN29553 and who meet the eligibility criteria. Accordingly, the sample size for this study is not based on a formal sample size calculation. The planned number of patients for this OLE study is not expected to exceed 1500 (approximately 750 randomized to crenezumab 60 mg/kg IV and 750 randomized to placebo, that is, the total planned number of patients in *the parent studies* BN29552 and BN29553, not including patients from the China extension study). An estimate for the actual number of patients in this OLE study is approximately 925 patients (*not including patients from the China extension study*) based on 1500 patients enrolled in both Phase III studies and an estimated reduction by 35% (i.e., withdrawals from double-blind treatment) and by a further 5% of completers who may not opt to enroll in this OLE study.

